# **Study Details**

### **Study Description:**

**Brief Summary:** 

Comparative randomized, single dose, three periods, three-way crossover open-label study to determine the bioequivalence of Valsartan and Amlodipine Tablets (Hua yuan Pharmaceutical LLC, China) and Valsartan and Amlodipine Tablets (I) (Novartis Pharma Schweiz AG, Switzerland).

Condition or disease	Intervention/treatment	Phase
healthy	Drug: Valsartan and Amlodipine Tablets	The bioequivalence
	Drug: Valsartan and Amlodipine Tablets	study

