## **Detailed Description:**

Primary Pharmacokinetic Parameters:  $C_{max}$ , Area under cover (AUC $_{0\rightarrow t}$  and AUC $_{0\rightarrow \infty}$ ). Secondary Pharmacokinetic Parameters:  $t_{max}$  and  $t_{1/2}$ . The method of judging bioequivalence of three-cross-section repeating experiment design: first of all, the calculation of the  $S_{WR}$  of the AUC and  $C_{max}$ , if  $S_{WR} \geqslant 0.294$ , the use of RSABE analysis; if Swr<0.294, the average Bioequivalence analysis method with Non-scale (bioequivalence limit is  $80\%\sim125\%$ ).

A comprehensive final report will be issued upon the completion of the study.

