### **Study Design:**

Study Type: Interventional (Clinical Trial)

Actual Enrollment: 84 participants

Allocation: Randomized

Intervention Model: Crossover Assignment

Masking: None (Open Label)

Official Title: Comparative Open-label, Randomized, Fasting/Fed, Single Dose, Three-way

Crossover Bioequivalence Study of Valsartan and Amlodipine Tablets (Hua yuan

Pharmaceutical LLC, China) and Valsartan and Amlodipine Tablets ( I ) (Novartis Pharma

Schweiz AG, Switzerland)

Study Start Date:

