**Arms and Interventions:** 

Arm	Intervention/treatment	
Experimental: T Test	Drug: Valsartan and Amlodipine Tablets	
Test drug(Valsartan / Amlodipine)1 tablet	1 tablet contains Valsartan 80mg&	
contains Valsartan 80mg& Amlodipine	Amlodipine 5mg	
5mg		
Active Comparator: R Reference	Drug: Valsartan and Amlodipine Tablets	
Reference drug(Valsartan / Amlodipine)1	(I)	
tablet contains Valsartan 80mg&	1 tablet contains Valsartan 80mg&	
Amlodipine 5mg	Amlodipine 5mg	

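### Does calling a two-product study a three-way crossover leave the S_WR decision rule without a repeated reference?

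*Protocol*

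**What the plan says.** The Brief Summary describes a "single dose, three periods, three-way crossover open-label study". The official title under Study Design also says three-way, and adds the meal conditions: "Comparative Open-label, Randomized, Fasting/Fed, Single Dose, Three-way". That section gives one enrolment figure, 84, described as actual, and a crossover intervention model. It gives no sequences and no split between fasting and fed.

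Arms and Interventions has two rows, "Experimental: T Test" and "Active Comparator: R Reference", both one tablet of valsartan 80 mg with amlodipine 5 mg.

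The Detailed Description introduces its decision rule as "The method of judging bioequivalence of three-cross-section repeating experiment design". The rule begins with "first of all, the calculation of the" S_WR for AUC and Cmax. At 0.294 or above it prescribes "the use of RSABE analysis"; below that, "the average Bioequivalence analysis method with Non-scale", with limits of 80% to 125%.

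**The concern.** In ordinary usage a three-way crossover gives three treatments once each. Here there are two products, and nothing says in words that the reference is given twice. S_WR can be estimated only from subjects with at least two reference periods. If each subject took the reference once, S_WR would have no degrees of freedom and the first step of the primary rule could not be run. The fasting/fed title raises the further thought that the three periods might be different conditions with no replication.

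Even if replication is granted, the text does not say which product is repeated. A partial replicate (TRR/RTR/RRT) and a two-sequence design (TRT/RTR) both have three periods, but they estimate S_WR with different precision. S_WR decides between fixed and scaled limits for the primary outcomes, so the choice bears on how often the wrong branch is taken.

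**Working it through.** The protocol gives no assumed variability, power or test-to-reference ratio, so it has no figure of its own to reproduce. The check has three parts.

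**1. Do the sections agree on a design?**

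- Brief Summary: three periods.
- Arms and Interventions: two products, T and R.
- Detailed Description: a repeating design, with S_WR computed first and a reference-scaled branch.

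Two products over three periods mean that each subject takes at least one product more than once. Six sequences contain both products: TTR, TRT, TRR, RTT, RTR and RRT. Three of them (TRR, RTR, RRT) give R twice. A rule that starts from S_WR requires at least one of these three. Together the sections therefore describe a three-period replicate crossover with the reference repeated. A non-replicated study would need a third treatment or a third condition; the document names neither, since fasting and fed are two conditions.

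The threshold is coherent with such a rule: CV = sqrt(exp(0.294²) − 1) = 0.300, the equivalent of a within-subject CV of about 30%.

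**2. Is S_WR estimable under the candidate designs?**

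- TRR/RTR/RRT: every subject contributes, df = N − 3.
- TRT/RTR, equal allocation: only the RTR half contributes, df = N/2 − 1.

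| Analysed N | TRR/RTR/RRT | TRT/RTR |
|---|---|---|
| 42 (assumes 84 split equally by meal condition) | 42 − 3 = 39 | 42/2 − 1 = 20 |
| 84 (assumes one combined study) | 84 − 3 = 81 | 84/2 − 1 = 41 |

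S_WR is estimable in all four cells.

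**3. How much does the unstated choice matter for selecting the branch?**

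Use df × S²/σ² ~ chi-square(df), with σ the true value. The true values 0.25 and 0.35 are illustrations, not protocol figures.

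- True 0.25: the estimate reaches 0.294 when chi-square(df) ≥ df × (0.294/0.25)² = df × 1.383.
- True 0.35: the estimate falls below 0.294 when chi-square(df) < df × (0.294/0.35)² = df × 0.7056.

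| Case | df 39 | df 20 | df 81 | df 41 |
|---|---|---|---|---|
| True 0.25, estimate ≥ 0.294 | 5.6% | 11.8% | 1.3% | 5.2% |
| True 0.35, estimate < 0.294 | 8.4% | 17.5% | 2.1% | 7.8% |
| 95% CI for σ at an observed 0.294 | 0.241–0.378 | 0.225–0.425 | 0.255–0.347 | 0.242–0.375 |

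These are chances of entering a branch. They are not error rates of the bioequivalence conclusion, which depend also on the product ratio and on the test applied within each branch.

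**The case for a change.** The strongest case for acting is that the number of times a subject takes each product, and in what order, is a basic design element. It governs dosing and randomisation as well as analysis, so a protocol should fix it and not leave it to a statistical analysis plan. The text that points to replication names neither the repeated product nor the sequences. Moving from TRR/RTR/RRT to TRT/RTR at least doubles the chance of landing in the wrong branch in every case computed above.

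Much of that stands as a drafting criticism. The label is imprecise, the sequences are not listed, and the relation of fasting and fed to the 84 participants is not given. The arithmetic is also right.

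It does not show a faulty plan, for three reasons. First, an arms table lists products, not administrations; a two-product replicate crossover has exactly two rows, so the lack of a second reference row contradicts nothing. Second, TRT/RTR also yields a valid S_WR; its lower precision is a trade-off between designs, not an error. Third, prescribing TRR/RTR/RRT with 1:1:1 allocation would be a guess. The document reports actual enrolment, and if TRT/RTR was used the new wording would be false.

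**Conclusion.** The concern does not call for a change to the plan. Three periods, two products, a design described as repeating and a rule that starts from S_WR all point to a three-period replicate crossover with the reference repeated. Only the term three-way is loose, in a text that reads as a translation. Analysts following the document would have repeated reference data and could run the rule as stated.

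The unstated choice of sequences affects the precision of S_WR: 39 against 20 degrees of freedom at 42 subjects, 81 against 41 at 84. The corresponding chances of taking the wrong branch run from 1.3% to 11.8% at a true value of 0.25, and from 2.1% to 17.5% at 0.35. These figures assume equal allocation to sequences and no dropout, and the 42 assumes an equal fasting/fed split that the document does not state.

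Recording the sequences actually used and the fasting/fed split would tidy the text. It would alter neither the analysis nor the decision rule.

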## **Detailed Description:**

Primary Pharmacokinetic Parameters:  $C_{max}$ , Area under cover (AUC $_{0\rightarrow t}$  and AUC $_{0\rightarrow \infty}$ ). Secondary Pharmacokinetic Parameters:  $t_{max}$  and  $t_{1/2}$ . The method of judging bioequivalence of three-cross-section repeating experiment design: first of all, the calculation of the  $S_{WR}$  of the AUC and  $C_{max}$ , if  $S_{WR} \geqslant 0.294$ , the use of RSABE analysis; if Swr<0.294, the average Bioequivalence analysis method with Non-scale (bioequivalence limit is  $80\%\sim125\%$ ).

A comprehensive final report will be issued upon the completion of the study.

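### Does the bioequivalence rule let a highly variable product pass with a mean ratio well outside 80-125%, because its RSABE branch prints no cap on the point estimate?

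*Protocol*

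**What the plan says.** The decision rule appears once, in the Protocol under Detailed Description. It is introduced as the way to judge bioequivalence in a "three-cross-section repeating experiment design". First sWR is calculated for AUC and Cmax. If sWR is at least 0.294, RSABE is to be used. If it is smaller, unscaled average bioequivalence is to be used, with 80% to 125% in brackets. The full wording from the scaled branch onward is "the use of RSABE analysis; if Swr<0.294, the average Bioequivalence analysis method with Non-scale (bioequivalence limit is", followed by that range.

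Nothing else in the Protocol adds to the rule. Outcome Measures lists bioequivalence on Cmax and on AUC without criteria. Study Design gives "Actual Enrollment: 84 participants" and a title covering both conditions, "Comparative Open-label, Randomized, Fasting/Fed, Single Dose, Three-way", without saying how the 84 divide between fasting and fed. No expected sWR is given for valsartan or amlodipine.

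**The concern.** The two branches look lopsided: one carries a numerical limit and the other only the name of a method. Read literally, 80-125% protects the conclusion when variability is low and disappears when it is high.

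That would matter because a reference-scaled criterion allows a difference in means proportional to sWR. Without a separate condition on the point estimate, a sufficiently variable reference could carry a product with mean exposure more than 25% away from the reference to a claim of bioequivalence. The rule decides the primary outcomes of an open-label study, so one would want it settled before the results are seen.

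**Working it through.** **What the text fixes.** The components of a scaled analysis, against the Detailed Description:

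| Component | In the Protocol |
|---|---|
| Method named | yes, RSABE |
| Switching value | yes, sWR 0.294 |
| Scaled criterion | not given |
| Scaling constant | not given |
| Confidence bound and its level | not given |
| Point-estimate cap | not given |

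The cap is missing in the same way as the three rows above it. The text neither says that the scaled bound is the only test nor rules out a point-estimate condition.

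**What must be added to obtain a rule that accepts large ratios.** The Protocol states no power or alpha figure to reproduce, so everything below rests on assumptions:
- partial replicate (T, R, R) in three sequences, df = n − 3, equal within-subject SD for test and reference, no subject-by-formulation interaction;
- n = 84, or n = 42 if the 84 divide equally between fasting and fed;
- scaling constant σ0 = 0.25 or, more strictly, 0.294;
- a one-sided 95% bound by Howe's approximation.

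Criterion: (mean T − mean R)² − θ·sWR² ≤ 0, with θ = (ln 1.25/σ0)². The implied limits are exp(±(ln 1.25/σ0)·sWR). At σ0 = 0.25, ln 1.25/σ0 = 0.893, so at sWR 0.50 the limits are exp(±0.446), or 64.0-156.3%.

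For an observed log ratio d:
- se² = 1.5·sWR²/n
- x = d² − se² and bx = (|d| + t·se)²
- y = −θ·sWR² and by = y·df/χ², with the 95% quantiles of t and χ² on df
- bound = x + y + √[(bx − x)² + (by − y)²]

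Example with n = 84, sWR = 0.50, σ0 = 0.25 and d = ln 1.3829 = 0.3242:
- se² = 0.375/84 = 0.00446, x = 0.1006, bx = (0.3242 + 1.664 × 0.0668)² = 0.1895
- y = −0.797 × 0.25 = −0.1992, by = −0.1992 × 81/103.0 = −0.1566
- bound = −0.0985 + √(0.0889² + 0.0426²) ≈ 0

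So 1.38 is the largest observed ratio that passes in this case. Over the range, without a cap:

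| sWR | Limits, σ0 0.25 | Largest ratio, n = 84 / 42 | Limits, σ0 0.294 | Largest ratio, n = 84 / 42 |
|---|---|---|---|---|
| 0.294 | 76.9-130.0% | 1.21 / 1.17 | 80.0-125.0% | 1.17 / 1.13 |
| 0.40 | 70.0-142.9% | 1.30 / 1.24 | 73.8-135.5% | 1.23 / 1.18 |
| 0.50 | 64.0-156.3% | 1.38 / 1.31 | 68.4-146.2% | 1.30 / 1.23 |
| 0.60 | 58.5-170.8% | 1.48 / 1.39 | 63.4-157.7% | 1.37 / 1.29 |

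Simulated pass rates at a true ratio of 1.30 (200,000 runs per cell; unscaled branch by 90% confidence interval), without cap → with cap:

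| sWR | σ0 0.25, n = 84 | σ0 0.25, n = 42 | σ0 0.294, n = 84 | σ0 0.294, n = 42 |
|---|---|---|---|---|
| 0.30 | 0.059 → 0.054 | 0.055 → 0.054 | 0.009 → 0.009 | 0.017 → 0.017 |
| 0.40 | 0.474 → 0.226 | 0.296 → 0.231 | 0.174 → 0.151 | 0.124 → 0.120 |
| 0.50 | 0.789 → 0.279 | 0.531 → 0.325 | 0.482 → 0.272 | 0.300 → 0.256 |

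**What this shows.** A cap can matter a great deal when sWR is high, and hardly at all near the switching value, where the bound alone keeps passing ratios inside 80-125%. But every cell needed a criterion, a constant and a bound that the Protocol does not print. If those are supplied as part of what RSABE means, the text gives no reason to stop short of the cap. If nothing is supplied, the branch contains no acceptance rule, so it cannot accept any product.

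**The contrast between the branches.** In the unscaled branch, 80-125% is the average-bioequivalence limit, applied here to the 90% confidence interval. A cap is a different condition, placed on the point estimate. A scaled analysis exists precisely so that the fixed limit is not applied to the interval when variability is high. Its absence from the scaled branch is therefore expected and says nothing about a cap.

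**The case for a change.** The strongest reply is that the Protocol chose to state the decision rule itself. It gives the switching value to three decimals and a numerical limit for one branch, so it may fairly be asked to finish the other. The criterion defines success on the primary outcomes of an open-label study, and the calculations confirm that an uncapped rule can pass an observed ratio above 1.25: from sWR of about 0.34 (n = 84) or 0.41 (n = 42) at σ0 = 0.25, and from about 0.43 or 0.53 at σ0 = 0.294.

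Two parts of this stand. The reading of the text is accurate, since no cap is printed. The arithmetic is also right for a rule without one. What does not follow is that the Protocol's rule is that rule. Naming a method and its switching value, and leaving its operating criteria to the analysis plan, is an ordinary division between the two documents. Giving the familiar limit for the unscaled branch does not turn silence about the scaled one into a statement that nothing further applies. A text that spelled out the scaled bound as sufficient and stopped there would be a different matter.

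**Conclusion.** This is not an error in the Protocol. The Detailed Description leaves the RSABE branch unelaborated but states nothing wrong in it and contradicts nothing elsewhere. The missing cap belongs with the missing criterion, constant and bound, all of which are commonly set out in the statistical analysis plan.

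The possible consequence ranges from nil near sWR 0.30 to a pass rate of 79% instead of 28% at sWR 0.50 (true ratio 1.30, n = 84, σ0 = 0.25). It belongs to an assumed uncapped rule, and with no expected sWR in the Protocol its likelihood for either analyte cannot be judged. The conclusion rests on the analysis plan not being at hand. It would change only if that plan made the scaled bound the sole test.

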### **Study Design:**

Study Type: Interventional (Clinical Trial)

Actual Enrollment: 84 participants

Allocation: Randomized

Intervention Model: Crossover Assignment

Masking: None (Open Label)

Official Title: Comparative Open-label, Randomized, Fasting/Fed, Single Dose, Three-way

Crossover Bioequivalence Study of Valsartan and Amlodipine Tablets (Hua yuan

Pharmaceutical LLC, China) and Valsartan and Amlodipine Tablets ( I ) (Novartis Pharma

Schweiz AG, Switzerland)

Study Start Date:

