### **Outcome Measures:**

Primary Outcome Measures:

Bioequivalence based on  $C_{max}$  [ Time Frame: Up to 96 hours post dose in each treatment period]

Bioequivalence based on AUC parameters [ Time Frame: Up to 96 hours post dose in each treatment period]

Secondary Outcome Measures:

Number of subjects with adverse events (AE)s [ Time Frame: Up to 96 hours post dose in each treatment period]

Safety and tolerability parameters will include recording of AEs

Safety assessed by vital sign measurement [ Time Frame: Up to 96 hours post dose in each treatment period]

Vital sign measurement will include blood pressure, pulse rate, respiration rate and ear temperature

Measure of clinical laboratory test values to access safety [ Time Frame: Up to 96 hours post dose in each treatment period]

Clinical laboratory tests will include blood biochemistry, CBC, urine routine examination and ECG.

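### Does naming fasting and fed dosing only in the official title commit the trial to one pooled bioequivalence verdict?

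*Protocol*

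**What the plan says.** The official title (Protocol, Study Design) reads "Official Title: Comparative Open-label, Randomized, Fasting/Fed, Single Dose, Three-way" and goes on to call the trial a crossover bioequivalence study. The same section gives "Actual Enrollment: 84 participants", with no breakdown.

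No other section names a meal condition:

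- Brief Summary: "Comparative randomized, single dose, three periods, three-way crossover open-label study to determine the bioequivalence of Valsartan and Amlodipine Tablets".
- Arms and Interventions: two entries, "Experimental: T Test" and "Active Comparator: R Reference", each a tablet of valsartan 80 mg and amlodipine 5 mg.
- Outcome Measures: one line for Cmax and one for AUC, the latter being "Bioequivalence based on AUC parameters [ Time Frame: Up to 96 hours post dose in each treatment period".
- Detailed Description: for AUC and Cmax, compute the reference within-subject SD (S_WR). Use reference-scaled analysis if it is at least 0.294; otherwise use "the average Bioequivalence analysis method with Non-scale" with limits of 80% to 125%.

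The only other text on diet is an exclusion criterion about special dietary needs, which does not define fasting or fed dosing.

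**The concern.** Read literally, the body describes one trial with one total, two arms, one pair of primary outcomes and one switching rule, while the title promises two meal conditions. If someone ran the rule once on all 84 participants, two things could go wrong.

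First, a pooled test/reference ratio averages a condition that is equivalent with one that is not. Second, the rule is a switch. A pooled S_WR can exceed 0.294 because one condition is variable, and so carry the less variable condition into the scaled branch when its own data would not qualify. Either way, equivalence could be claimed although one condition named in the title fails.

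**Working it through.** **1. Is there a stated figure to reproduce?** Only the enrolment of 84. The document gives no alpha, power, within-subject SD, expected ratio or dropout rate, so 84 cannot be re-derived. No statement about precision rests on it either.

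**2. What does the design imply?** The Brief Summary fixes three periods. The Detailed Description ties the rule to a three-period replicate design, and S_WR needs the reference at least twice in the same subject. Two reference doses plus one test dose make 2 + 1 = 3 periods, so no period is left for a second meal state. Giving the two reference doses under different meal states would put the food effect into S_WR. Fasting and fed must therefore be two crossovers, each in one meal state, and a rule written for such a crossover applies to each.

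**3. Does silence mean merging?** The rule is just as silent on analyte, although the tablet contains two drugs. Nobody would form one S_WR from valsartan and amlodipine concentrations together. The rule is a generic recipe, repeated for each comparison. With two conditions, two analytes and three primary parameters (Cmax and the two AUCs), that is 2 × 2 × 3 = 12 applications.

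**4. What would pooling do if it were done?** Assumptions, none from the protocol: sequences TRR/RTR/RRT; contrast T minus mean of R with SE = √(1.5·s²/n) and n − 3 degrees of freedom; 90% interval against 80% to 125%; s = 0.25; true ratios 1.00 and 0.75; 42 per condition.

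- Failing condition alone, n = 42: SE = √(1.5 × 0.0625/42) = 0.0472. The expected interval is exp(ln 0.75 ± 1.685 × 0.0472) = 0.693 to 0.812, and the pass probability is about 0.1%.
- Pooled, n = 84: ratio exp((ln 1.00 + ln 0.75)/2) = 0.866 and SE = √(1.5 × 0.0625/84) = 0.0334. The expected interval is 0.866 × exp(±1.664 × 0.0334) = 0.819 to 0.916, and the pass probability is about 76%.

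Pooled pass probability under the same assumptions, by split of the 84:

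| Equivalent / failing condition | Pooled ratio | Pooled pass |
|---|---|---|
| 28 / 56 | 0.825 | 24% |
| 36 / 48 | 0.848 | 54% |
| 42 / 42 | 0.866 | 76% |
| 48 / 36 | 0.884 | 91% |
| 56 / 28 | 0.909 | 98% |

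At 42/42, varying s from 0.15 to 0.29 moves the pooled figure from 99% to 65%; the failing condition alone never exceeds 0.3%.

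For the switch, take fasting ratio 1.25 with SD 0.25 and fed ratio 1.00 with SD 0.40. The pooled S_WR is √((0.25² + 0.40²)/2) = 0.334, above 0.294. In simulation the pooled analysis used the scaled branch in about 91% of trials, against about 6% for the fasting data alone.

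**5. Is there pressure to pool?** Little, under these assumptions. With a true ratio of 0.95 in both conditions, 42 each and unscaled limits, the pass probability per condition for one parameter is 97.3% at s = 0.25 and 92.4% at s = 0.29. For independent cohorts, both pass in 0.973² = 94.7% and 0.924² = 85.4% of trials. Separate verdicts are workable at this size.

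**The case for a change.** The strongest case for acting is that the number of participants in each meal condition is a design fact rather than an SAP detail, and that the title and the body of the same document do not match. A protocol should say which comparisons make up success. Under an assumed equal split, ratios of 1.00 and 0.80 and SD 0.25, both conditions pass separately in about 6% of trials while pooled data pass in about 94%. In the scenarios built that way, splits of 36/48 or 48/36 still leave pooled pass rates between 86% and 99%. Writing the separation down would cost only wording.

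The gap in reporting stands: the split is not given and separate judgement is not stated. The arithmetic also stands as a description of pooling. What does not follow is that the plan pools. Every adverse figure needs an analysis that no section states, and a difference of 20% or more between the meal conditions in the test/reference ratio, for which the document gives no basis. Nor does 84 overstate precision, because it is reported as total enrolment and no claim is built on it.

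**Conclusion.** The mismatch is real but minor: fasting and fed appear only in the title, and the 84 are not divided. The protocol neither prescribes nor excludes pooling. Its three-period replicate design leaves no room for two meal states within a subject, so running the switch and the equivalence test within each condition, and for each analyte, fits the text without altering any stated rule. This is missing detail that analysts would fill sensibly or that an SAP would carry; it is not a rule that gives a wrong answer.

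The pooled pass rates (24% to 98% across splits at SD 0.25 with ratios 1.00 and 0.75) show why separate analysis is the sensible reading. They rest on assumed ratios, SDs and splits and are not evidence that pooling is planned. The conclusion would change only if an SAP or report were found to compute one S_WR or one ratio across both meal conditions.
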